## 7.1 Primary Objective

- To evaluate the impact of the CAD system on endoscopists' detection of colorectal polyps
- To evaluate the impact of CAD characterisation system on endoscopists performance in optical diagnosis of diminutive colorectal polyps compared to histology

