## 8.1 Summary of Study Design

This will be a multi-centre randomised control superiority trial. Participants will be randomised to either standard colonoscopy (control arm) or colonoscopy plus WISE VISION® CAD device (intervention arm). The CAD device has both detection and characterisation functions and there are 2 elements within the study. Firstly the study will aim to assess the impact of computer aided detection and secondly computer aided characterisation.

When polyps are identified, these will be recorded and the endoscopist will be required to assess this and indicate their optical diagnosis accordingly. For patients randomised to colonoscopy plus CAD, the CADx will then be carried out and the results recorded. Polyps will be treated according to standard care.

Polyps detected by the endoscopists but missed by the CADe device will also be recorded. The total number of polyps identified and the endoscopist diagnosis will be recorded for both arms. The histology results of the polyps removed will be collected.

Figure 1: Study Procedure Flowchart

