## 8.2 Primary and Secondary Endpoints/Outcome Measures

## **Primary End points**

Adenoma detection rate in both arms PIVI-2: NPV of adenoma diagnosis in diminutive (<5mm) recto-sigmoid polyps in both arms

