### 11.3 Randomisation

Participants will be randomised electronically in a 1:1 ratio into two groups. The intervention group will have their colonoscopy performed with the assistance of the WISE VISION® CAD system, the control arm will have standard colonoscopy. Randomisation will be carried out prior to the procedure being started. The randomisation will be stratified by site to ensure an equal allocation in each centre. Additionally, a blocked randomisation, with varying block sizes, will be performed to allow for a balance between groups throughout the trial.

The randomisation process will be managed using the built-in module within the project's REDCap eCRF database managed by Portsmouth Hospitals University NHS Trust. The Data Manager will generate the randomisation allocation table using statistical software, which will then be uploaded into REDCap before the first patient is consented.

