## 11.4 Study Assessments

Baseline characteristics will be recorded for all participants. Basic demographics will be recorded to include:

- Age
- Sex
- Co-morbidities and ASA score
- History of previous polyps/bowel conditions

During the colonoscopy the following will be recorded in all patients:

- Endoscopist including level of experience (number of life time procedures)
- Indication
- Bowel preparation used and quality
- Use of sedation/general anaesthetic
- Procedure start and finish time and time of maximal intubation
- Comfort score
- Adverse events
- Polyps detected to include the endoscopists optical diagnosis and assessment of size, morphology using the Paris classification, site and details of their removal.
- Still image/video of polyp (where available)

For patients randomised to colonoscopy plus CAD the following additional data will be recorded:

- Total number of potential polyps identified by CADe
- CADx diagnosis of polyps identified
- Outcome of assessment by endoscopist e.g. confirmed as polyp, characterisation assessment

Post colonoscopy:

- Adverse events will be recorded
- Histology of any polyps removed will be recorded to correlate with the endoscopist/CADx assessment of the lesion.

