#### 14.2 Analysis of Endpoints

The primary outcome, ADR, will be compared between groups using the Chi-square test. The difference in the proportion of patients with an adenoma detected between groups will be quantified, along with a corresponding 95% confidence interval.

Within both groups, a descriptive analysis of percentage of polyps correctly identified, relative to the histological diagnosis, will be reported.

For all detection outcomes, a series of sensitivity analyses will be performed, repeating the analyses, but this time only considering polyps in the CAD intervention group if they were correctly identified based on their histology.

Binary secondary outcomes will be analysed using the Chi-square test. Continuous secondary outcomes will be compared between groups using the unpaired t-test, if found to be normally distributed, or the Mann-Whitney test otherwise.

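### The protocol does not keep the trial arm, the optical diagnosis or the CADx output from the pathologist whose report is the reference standard for the NPV primary endpoint

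*Protocol*

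**What the plan says.** Protocol section 7.1 makes it a primary objective to evaluate endoscopists' "performance in optical diagnosis of diminutive colorectal polyps compared to histology". The matching primary endpoint in section 8.2 is "NPV of adenoma diagnosis in diminutive (<5mm) recto-sigmoid polyps in both arms". The other primary endpoint is ADR, analysed in section 14.2: "The difference in the proportion of patients with an adenoma detected between groups will be quantified". The protocol does not spell out that an adenoma must be confirmed histologically, but histology is the only tissue diagnosis it collects.

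On how the reference is obtained, section 8.1 says "Polyps will be treated according to standard care" and "The histology results of the polyps removed will be collected". Section 11.4 adds "Histology of any polyps removed will be recorded to correlate with the endoscopist/CADx assessment of the lesion". Section 11.6 allows time at the end of the study for histopathology reporting.

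The calls to be judged are made during the procedure, before histology. Section 11.4 lists the endoscopist's optical diagnosis among the items recorded in all patients. In the intervention arm there is a further call: "For patients randomised to colonoscopy plus CAD, the CADx will then be carried out and the results recorded" (section 8.1).

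Neither section 11.3 on randomisation nor section 14 on analysis contains a masking statement for any party. No section describes a second or central reading of histology, or says what may accompany a specimen to pathology.

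**The concern.** The endoscopist necessarily knows whether the CAD display is in use. The pathologist is therefore the one assessor of adenoma status who can be independent of the arm and of the optical call. The protocol does not secure that independence: a site that wrote the optical diagnosis or the CADx output on the request form would breach nothing in it.

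NPV is the share of polyps called non-adenoma that histology confirms as non-adenoma. A pathologist who sees a non-adenoma call on a small, equivocal specimen may lean towards it. Each adenoma among the negative calls that is reported as non-adenoma turns a diagnostic error into an apparent success. At stake are the absolute reading of NPV against the 90% PIVI threshold in the synopsis hypothesis, and the comparison of NPV between arms. Once reports have been issued with the call in view, no analysis can undo it.

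**Working it through.** **Inputs from Protocol section 10.** NPV 75% (endoscopist) vs 90% (endoscopist plus CADx), power 80%, alpha 0.05, 100 diminutive recto-sigmoid polyps per group. Sidedness is not stated; two-sided reproduces the plan's figure. As in the plan's calculation, 100 per arm is taken as the NPV denominator and polyps are treated as independent.

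**Input assumed.** f is the share of true adenomas among negative calls that is reported as non-adenoma because the call was visible. The documents give no value, so a range is shown.

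**Step 1: the plan's own figure.** n per arm = [1.96·√(2·p̄·(1−p̄)) + 0.8416·√(p₁(1−p₁) + p₂(1−p₂))]² / (p₂−p₁)². With p₁ = 0.75, p₂ = 0.90 and p̄ = 0.825: (1.0532 + 0.4433)² / 0.0225 = 99.5, so 100 per arm. The stated size reproduces, and power at 100 per arm is 80.2%.

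**Step 2: effect of drift on one arm's NPV.** Observed NPV = 1 − (1 − true NPV)(1 − f).
- True 75%, f = 0.20: 1 − 0.25 × 0.80 = 80%.
- True 90%, f = 0.20: 1 − 0.10 × 0.80 = 92%.
- An assumed true 85% would be observed as 88% at f = 0.20 (1 − 0.15 × 0.80). It would be observed as 90%, the threshold, at f = 0.05/0.15 = 1/3.

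**Step 3: effect on the comparison.** Power = Φ{[d − 1.96·√(2·p̄·(1−p̄)/100)] / √([p₁(1−p₁) + p₂(1−p₂)]/100)}, where p₁, p₂ and p̄ are the observed values and d = p₂ − p₁.
- Drift of 20% in both arms, true 75% vs 90%: observed 80% vs 92%, d = 0.12. (0.12 − 1.96 × 0.04907)/0.04833 = 0.493, so power is 68.9%.
- Drift of 20% in the CAD arm only, true 75% in both: observed 75% vs 80%, d = 0.05. (0.05 − 1.96 × 0.05906)/0.05895 = −1.115, so the chance of a significant result in favour of CAD is 13.2%.

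| f | Both arms drift, true 75% vs 90%: observed | Power | CAD arm only, true 75% in both: observed CAD NPV | False result in favour of CAD (nominal 2.5%) |
|---|---|---|---|---|
| 0.10 | 77.5% vs 91% | 74.9% | 77.5% | 6.1% |
| 0.20 | 80% vs 92% | 68.9% | 80% | 13.2% |
| 0.30 | 82.5% vs 93% | 62.1% | 82.5% | 25.3% |

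**Step 4: direction of the contrast.** Under the plan's rates, the observed difference in points is (90 + 10·f_CAD) − (75 + 25·f_control) = 15 + 10·f_CAD − 25·f_control. It exceeds the true 15 points only if f_CAD is more than 2.5 times f_control. Otherwise it is unchanged or shrinks.

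**Step 5: ADR.** A visible adenoma call could move borderline tissue to adenoma and raise ADR. A visible non-adenoma call could move an adenoma the other way and lower it. Both kinds of call exist in both arms, so the net sign cannot be derived.

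**The case against.** The strongest reply is that this rests on silence. No section mentions a pathology request form or sends the calls to pathology. Section 13 routes them to a paper CRF and then to a REDCap database with site logins and an approved user list. The study flowchart is not reproduced in the text at hand, and a local procedure might cover the point. This limits the claim: the documents show that drift is permitted, not that it will happen. It does not remove the claim, because data-entry routing is not a masking rule and no pathology procedure is cited.

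A reader might go further and infer that any such bias favours the device on both primary endpoints, particularly as the manufacturer funds the trial. The documents do not support that. The optical diagnosis is recorded in all patients, so drift from it could occur in both arms, and equal drift narrows the NPV contrast and costs power. Bias towards the device requires drift in the CAD arm to be sufficiently larger, and the documents give no ground for a size. For ADR the direction is open. The funding source is no evidence about how histology is read, and no section gives the funder a part in it.

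It is also fair that every misreading rate here is assumed, and that a remedy stripping the request form to a few items would sit badly with the protocol's commitment to standard care (synopsis; Adherence to Study Treatment). Both objections stand, and they shape the fix. The absence of an SAP does not answer the point, since what a pathologist is told is study conduct.

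**Conclusion.** The point holds as an unprotected reference standard. It is most direct for NPV, where the call and the histology concern the same polyp. It is weaker for ADR, whose dependence on histology is implied and whose bias has no determinable sign. If the calls are visible, NPV in either arm can be inflated against the 90% threshold, and the between-arm contrast can move either way.

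The computed sizes are illustrations. At 20% drift, the consequence ranges from a loss of about 11 points of power (80% to 69%, both arms) to a false result in favour of CAD about 13% of the time (CAD arm only, no true difference). They rest on an assumed misreading share, on drift only from adenoma to non-adenoma among negative calls, and on the plan's 100 polyps per arm. No stated figure in the protocol is wrong and the sample sizes do not change. This is a cheap improvement to make before reports are issued, not a demonstrated bias.

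**What to change.** Add to section 11.4, in substance: for trial polyps, the randomised arm, the endoscopist's optical diagnosis and the CADx output are not given on the pathology request or any accompanying report until the histology report has been issued. All other routine clinical information is supplied as usual. Any disclosure judged clinically necessary is made and recorded in the CRF.

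The cost is a small change to how request forms are completed at each of the seven listed sites. No extra reader, repeat histology or change in sample size is needed.

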## 11.5 Discontinuation/Withdrawal of Participants from Study Treatment

Participants are free to withdraw their consent at any point during the study if they wish. Data collected up to the point of withdrawal will still be included in the analysis.

The withdrawal of a participant in the study will also be required in the following situations:

- obstructing lesions
- inability to complete the procedure e.g. difficult colonoscopy

## 11.6 Definition of End of Study

The study will end 28 days(+/- 14 days) after the last participant has been recruited to allow for the reporting and collection of histopathology data. Patients will be followed up as per standard management, judged by the endoscopists (for example as per polyp surveillance guidelines). There is no additional follow up required.

## 11. INTERVENTIONS

#### 11.1 Description of Study Intervention / Treatment

Colonoscopy is the gold standard technique for examination of the large bowel. Because of the knowledge of the long term risks polyps developing into cancers, when there are identified during colonoscopy it is standard practice to remove them where indicated and safe to do so. Removal of polyps is dependent on first identifying them, and secondly being able to accurately diagnose the type of polyp.

The use of Computer Aided Detection and Diagnosis (CAD) with the WISE VISION® is the intervention in this study. This is a CE marked device designed to improve both detection and diagnosis of polyps. The intervention in this study therefore aims to enhance polyp detection and diagnosis. Patients who do not consent to take part will still be treated in the same way.

# 11.2 Adherence to Study Treatment

All patients undergoing colonoscopy are managed according to local and national guidelines including the decision to remove polyps and the follow up following the procedure. Given this, management of patients and adherence to treatment should not be altered as a direct result of this trial.

## **12. ASSESSMENT OF SAFETY**

#### 12.1 Definitions

### Adverse Event (AE)

Any untoward medical occurrence in a patient taking part in a clinical trial which does not necessarily have to have a causal relationship with the device under investigation.

#### Adverse Device Effect (ADE)

Adverse Device Effects (ADEs) are all untoward and unintended medical occurrences in response to a medical device.

All cases judged by either a medically qualified professional or the sponsor as having a reasonable suspected causal relationship to the device qualify as a device effect.

This also includes any event resulting from insufficiencies or inadequacies in the instruction for use or deployment of the device and includes any event that is a result of a user error.

### Serious Adverse Event (SAE)

A serious adverse event is any untoward medical occurrence that:

- Results in death,
- Is life-threatening,

NOTE: The term "life-threatening" in the definition of "serious" refers to an event in which the participant was at risk of death at the time of the event; it does not refer to an event which hypothetically might have caused death if it were more severe.

- Requires inpatient hospitalisation or prolongation of existing hospitalisation,
- · Results in persistent or significant disability/incapacity, or
- Is a congenital anomaly/birth defect.
- Other important medical events\*

\*Other events that may not result in death, are not life threatening, or do not require hospitalisation, may be considered a serious adverse event when, based upon appropriate medical judgement, the event may jeopardise the participant and may require medical or surgical intervention to prevent one of the outcomes listed above.

To ensure no confusion or misunderstanding of the difference between the terms 'serious' and 'severe', which are not synonymous, the following note of clarification is provided:

The term 'severe' is often used to describe the intensity (severity) of a specific event (as in mild, moderate or severe myocardial infarction). The event itself however, may be of relatively minor medical significance (such as severe headache).

This is not the same as 'serious', which is based on patient/event outcome or action criteria usually associated with events that pose a threat to a participant's life or functioning. Seriousness (not severity) serves as a guide for defining regulatory reporting obligations.

## A non-CTIMP Suspected Unexpected Serious Adverse Reaction (SUSAR)

is defined as any Serious Adverse Event judged to be:

• Related to the administration of any intervention or any study procedure of interest to the study i.e. having a reasonable causal relationship to that procedure or intervention

• Unexpected, i.e. not listed in the protocol (or product information) as an expected occurrence for those specified procedures/intervention, and

• Unrelated to the administration of an IMP i.e., having no reasonable causal relationship to an IMP

## 12.2 Reporting Procedures for Serious Adverse Events

All SAE/SADEs occurring to a participant will need to be initially recorded in the study CRF and reported to the Chief Investigator and Sponsor (unless exempt from being reported) in line with PHT/RDSOP/007 – SOP for Investigators: Recording, Assessing and Reporting Adverse Events in Clinical Research (found at http://www.porthosp.nhs.uk/Research-Department/policies.htm). All assessments shall be made in accordance with this SOP and all recorded adverse event data shall be collated and included in the study analysis. Listings of adverse events will be provided to the Sponsor by the TMG/TSC, when requested, for safety oversight.

## Exemptions to SAE reporting:

Complications arising from colonoscopy or polypectomy (bleeding, perforation, etc.) would not be classed as adverse events of the study, and therefore for the purpose of the study would not be considered to be reportable SAEs. In the event these occur they should still be recorded in the study CRF. These include the following:

- Bleeding: this includes intra procedural, early or delayed bleeding.
- Perforation
- Hospital admission
- Missed pathology
- Recurrence of pathology
- Death

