# 7.2 Secondary Objectives

- To assess the diagnostic performance of the CAD system on detection of colorectal polyps according to their size, location and morphology
- To evaluate the diagnostic performance of the CAD system on characterization of colorectal polyps based on size, location and morphology
- Evaluate the false positives and false negatives by the CADe system to understand predictors of wrong CADe detection
- Evaluate the cost implications of the CAD system
- Evaluate the impact of the CADe system on complications from colonoscopy and polyp removal

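### The SAE exemption removes procedural complications from the adverse events by type, with no exception for suspected device effects, and so conflicts with the protocol's own safety definitions

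*Protocol*

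**What the plan says.** The protocol deals with complications in five places.

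- **Section 12.1, Adverse Event.** An AE is any untoward medical occurrence in a participant, "which does not necessarily have to have a causal relationship with the device under investigation".
- **Section 12.1, Adverse Device Effect.** All cases judged "as having a reasonable suspected causal relationship to the device qualify as a device effect". User error is expressly included.
- **Section 12.1, Serious Adverse Event.** Death and inpatient hospitalisation are both seriousness criteria.
- **Section 12.2.** "All SAE/SADEs occurring to a participant will need to be initially recorded in the study CRF and reported to the Chief Investigator and Sponsor", with a proviso in brackets that excludes events exempted from reporting. The same section says that the recorded adverse event data will be collated and analysed.
- **Exemptions to SAE reporting (within 12.2).** Complications of the procedure "would not be classed as adverse events of the study, and therefore for the purpose of the study would not be considered" as SAEs that need reporting. The list names bleeding, perforation, hospital admission, missed pathology, recurrence of pathology and death. It adds: "In the event these occur they should still be recorded in the study CRF".

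Section 7.2 has a related secondary objective: "Evaluate the impact of the CADe system on complications from colonoscopy and polyp removal".

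**The concern.** Exempting expected procedural complications from SAE reporting can be a reasonable choice. This exemption does two further things. It depends only on the type of event, so a listed event is exempt even when the device is the suspected cause. It also removes the events from the class of adverse events altogether, which is more than waiving a reporting step.

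Both matter for a device that works only during colonoscopy. A harm it causes would usually also be a complication of colonoscopy or polypectomy, for example a perforation at a polypectomy that a CADe alert prompted. At stake are the reporting of suspected device effects to the Sponsor and the place of these complications in the safety analysis.

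**Working it through.** The protocol gives no complication rate, so there is no figure to reproduce. The check sets the sections side by side.

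1. **AE definition against exemption.** Section 12.1 defines an AE without regard to cause, so a post-polypectomy bleed is an AE. The exemption says it is not an adverse event of the study. Both cannot hold.

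2. **SAE criteria against exemption.** By 12.1, death and inpatient admission are serious. The exemption lists both, when they arise from the procedure, as neither adverse events nor reportable SAEs. Waiving the report is compatible with 12.1; declassifying the event is not.

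3. **Device-effect definition against exemption.** Section 12.1 takes in every case with a reasonable suspicion of device causation. The exemption has no matching condition. A perforation after a CADe-prompted removal fits both texts: a device effect under one, not an adverse event under the other.

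4. **Does the exemption reach device effects?** Its own text names only SAEs. But the reporting rule in 12.2 covers SAEs and SADEs together, and its proviso for exempt events applies to both. (SADE has no entry in 12.1; it is read here as a serious device effect.) Nothing in the list brings suspected device-related cases back into reporting.

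5. **Does the SUSAR route close the gap?** Section 12.3 keeps reporting to the Sponsor within 24 hours for SUSARs. Under 12.1 a SUSAR must be unexpected, meaning not listed in the protocol or product information as an expected occurrence. The exemption list does not use the word expected, but a site could reasonably read a protocol list of recognised complications that way. The route may therefore fail for exactly these events.

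6. **Are the data kept?** Yes. The exemption requires CRF recording, and section 11.4 has adverse events recorded in all patients during colonoscopy and again afterwards. A comparison of complications by arm is possible.

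7. **Do the data reach the analysis?** Section 12.2 commits adverse event data to it. The exemption says these events are not adverse events. Taken literally, the two together leave the complications recorded but outside the promised analysis.

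8. **Could exposure differ by arm?** Section 10 assumes that ADR rises from 20% to 30%. With the powered 294 per group, 294 × (0.30 − 0.20) = 29.4. With the maximum of 654 / 2 = 327 per group, 327 × 0.10 = 32.7. So about 29 to 33 more patients in the CAD arm would have an adenoma found, and the description of the intervention (second section numbered 11.1) says that removal where indicated and safe is standard practice. This shows why exposure to polypectomy need not be equal between arms. It is not a count of complications or of unreported events.

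**The case against.** The strongest reply is that the exemption is a deliberate choice about reporting and that no data are lost. It covers only complications that arise from the procedure, so not every death or admission is exempt. It speaks of SAEs and does not say that the device-effect definition is set aside. Section 18 has the TSC review safety events, with oversight by the Sponsor's research governance team. Section 12.2 provides adverse event listings to the Sponsor on request, and reporting follows an SOP that is not shown. How complications are tabulated is commonly left to the SAP.

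Much of this stands, and it rules out three stronger readings.

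- **That the exemption contradicts the objective in section 7.2.** It does not. That objective needs complication data in both arms, and the CRF holds them. What remains is an uncertainty over whether they enter the analysis.
- **That a device-related harm or death would not reach the Sponsor or TSC in time.** The protocol does not show this. TSC review exists, and the SOP may add safeguards. What can be said is that the protocol text permits non-reporting and leaves unclear whether exempted events count as safety events for the TSC.
- **That the 29 to 33 patients measure the harm.** They are adenoma-positive patients under the planning assumption, not events.

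The reply does not remove the core. The protocol states a rule that conflicts with its own definitions, so this is not a detail left to the SAP. The proviso in 12.2 extends that rule to SADEs.

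**Conclusion.** The point holds as a conflict within section 12. The exemption contradicts the AE definition, is incompatible with the SAE criteria in so far as it declassifies serious events, and leaves a listed event with suspected device causation both a device effect and not an adverse event. A suspected device-related complication could go unreported to the Sponsor, and on a literal reading the exempted complications drop out of the analysis that 12.2 promises.

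Its size cannot be put in numbers, because no complication rate is given. The conclusion assumes that the proviso in 12.2 refers to the exemption list directly below it, and that SADE means a serious device effect. The concern about the SUSAR route also assumes that listed events are read as expected. The unseen SOP could narrow the reporting gap in practice, but it would not resolve the conflict in the protocol's wording. The point should be corrected. It does not touch the primary endpoints or the sample size.

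**What to change.** Reconcile section 7.2, the AE, device-effect and SAE definitions in 12.1, the reporting rule in 12.2 and the exemption list. Three changes do this:

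1. State that the exemption does not extend to a listed event with a suspected causal relationship to the device; such an event follows the SADE reporting in 12.2.
2. Replace the statement that the listed complications are not adverse events of the study with one that they are exempt from SAE reporting.
3. State that all listed complications recorded in the CRF are tabulated by arm for the TSC and in the final analysis.

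A demand that every death be reported would go beyond reconciling the text and is not part of this point. The cost is a few sentences, one by-arm table and a few more reports to the Sponsor. The design and the data collection do not change.
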